9. ETHICAL ASPECTS

9.1 ETHICAL AND REGULATORY REQUIREMENTS

The study will be carried out in accordance with the protocol, the ethical principles based on the latest version of the Declaration of Helsinki (WORLD MEDICAL ASSOCIATION DECLARATION OF HELSINKI. (Ethical Principles for Medical Research Involving Human Subjects) (Annex III), in the Guidelines of the International Conference on Harmonization (ICH) on Good Clinical Practice (ICH Topic E: Good

Clinical Practice. Note for Guidance on Good Clinical Practice. CPMP / ICH / 135/95 and to any new version or modification existing; as well as applicable national and / or international legislation.

9.1.1 Investigator Responsibilities

Before starting the study, the Investigator must sign a protocol signature page confirming that you agree to carry out the study in accordance with these documents and with all the instructions and procedures described in the protocol and that, when required, will allow designated monitors, representatives of the Warranty Department of Clinical Quality (CQA) and the Health Authorities have access to all the data and relevant records.

The Investigator is responsible for providing patients and / or their representatives with adequate oral and written information about the study. All questions about the study must be answered to the patient and / or their legal representatives.

9.1.2 Informed Consent

Eligible patients can only be included in the study after providing for written informed consent previously approved by the CEIC (Annex II), or, in the case of inability to do so, after said consent has been granted by a legal representative of the patient, or in the event that he lacks a legal representative the person linked to the patient for family reasons. Informed consent must be signed and dated by the patient and the investigator, who will have provided each patient (or a representative of the patient) prior to inclusion in the study, information complete and adequate verbal and written study objectives and procedures, as well as as the possible risks that it may entail. The bone marrow donor will thus receive himself, an information sheet and will sign a consent authorizing the use of his cells for allogeneic transplantation (see Annex II). Informed consent must be obtained before starting any procedure. study specific (i.e. all procedures described in the protocol). The process of obtaining informed consent must be recorded in the documents patient source.

The proposed informed consent forms are provided in ANNEX II. that meets regulatory requirements and is deemed appropriate for this study. The informed consent / patient information sheet includes the items listed in the ICH Guideline on Good Clinical Practice. Any change in the Informed consent proposed by the investigator must be approved by the Promoter and notified to the corresponding CEIC.

9.1.3 Approval of the Clinical Research Ethics Committee (CEIC)

Before starting the study, the written, signed and dated approval of the protocol, informed consent and patient information sheet by the CEIC applicable according to current national legislation. The approval must be saved in the file of the researcher in the center and a copy in the file of the Promoter.

9.1.4 Approval of the Health Authorities

Before starting the study, all established regulatory requirements must be met and the clinical trial must be approved. The Promoter or representative of the Promoter together with the Researcher will request the approval of the Health Authorities. This approval is will be kept in the Researcher's file at the study center, with a copy in the file of the Promoter.

9.2 MODIFICATIONS OF THE PROTOCOL

Any changes or additions to this protocol can only be made through a Written amendment to the protocol, which must be approved by the AEMPS and CEIC corresponding, when required according to current applicable legislation. All amendments to the study protocol will be made in writing and filed in the corresponding study file, as a modification of the protocol. Are Modifications must be documented, dated and signed by the investigator and the Promoter.

9.3 INSURANCE POLICY

The promoter of the study, will arrange an insurance that covers the damages and losses that as a consequence of the same could result for the person in which it is to be carried out: Said civil liability insurance will cover the responsibilities of the Promoter, the researcher and his collaborators and the head of the hospital or center

where the trial is carried out and will comply with current applicable legislation. Policy is attached.

9.4 ACCESS TO PATIENT DATA

The patient's medical information obtained by conducting this study is considered confidential and its disclosure to third parties is prohibited. The confidentiality of the patient is insured since they will be identified only by their initials and a code number of the assigned study.

The investigator will inform patients that their identity will be strictly maintained confidential. During the study, the patient will be guaranteed strict compliance with the Law 15/1999 of December 13, Protection of Personal Data. The researcher, when processing and treating the patient's data, will take the necessary measures appropriate to protect them and prevent access to them by unauthorized third parties. The patient may revoke the informed consent for the processing of their data personal, addressing the investigator.

The data generated as a result of the clinical trial must be available to be inspected at the request of the Promoter, the CEIC or the Health Authorities. The signing of the informed consent means that the patients explicitly accept that the study data may be consulted by the researcher and his team, the representatives of the Promoter and if required by the CEIC and Health Authorities.

10. PRACTICAL CONSIDERATIONS

10.1 RESPONSIBILITIES OF THE VARIOUS PARTICIPANTS IN THE TRIAL 10.1.1 Investigator

The researcher must comply with all the requirements of the protocol, he will be responsible for the information is accurate and truthful and has been obtained in the manner indicated therein. In particular, the investigator must ensure the best possible care at all times. of the patient always putting their safety and well-being first.

10.1.2 Monitor

The monitor must confirm that the information collected in the CRD is true, for which must have the collaboration of the research team. In addition, you will be responsible for communicate to the Sponsor any serious or unexpected adverse events that occur during the study.

10.1.3 Promoter

The Promoter will be responsible for ensuring compliance with the ICH Directive on Good Clinical Practice and applicable national and / or international regulations.

10.2 DATA REVIEW

10.2.1 Center monitoring

Before starting the study, a meeting of the monitor will be held with all the investigators and the protocol and the correct composition of the CRDs will be reviewed. During the study, the monitor designated for the test will regularly visit the entrance to check that patient documents are complete, data accuracy of the CRDs, the monitoring of the Standards of Good Clinical Practice (GCP) and the progress of recruitment. Investigators and all personnel involved in the trial should be available to assist the monitor during these visits.

The researcher must make available to the monitor the source documents of each study patient that will consist of the history and notes of the visit (medical records, clinical or hospital) including medical and demographic information, data from laboratory and the results of any other tests or evaluations. All the information that is registered in the CRDs, it must be verifiable with the source documents that they are usually found in the patient's medical record. The investigator must keep a copy of the signed informed consent form.

The researcher must agree to the monitor reviewing all source documents for confirm that the data is consistent with the data in the CRDs. A complete verification of the existence and correct obtaining of informed consent, of the compliance with the inclusion / exclusion criteria, the documentation of the AAGs and the record of the data

used for all efficacy and safety variables. I know carry out additional checks of the consistency of the original data with

those of the CRDs, according to the study's specific monitoring plan.

10.3 DATA COLLECTION

10.3.1 Data collection notebook (CRD)

All the data generated in the clinical part of this study will be transcribed in the CRDs they will be printed in triplicate (carbonless paper). All data will be transcribed and modifications will be made in black ink. Any correction of the data must be signed, dated and with the reason for the modification noted. Only authorized personnel can enter data and make corrections in the CRD. The Investigator and study monitor will review all CRDs to ensure they are complete and legible and accurate. The monitor will instruct the center staff to make any necessary corrections or additions. The study monitor will have access to the medical records, original laboratory data and other related documents with the study, without compromising the identity of the patients. CRDs should be completed on a regular basis to keep data up to date and reflect the patient's condition in each period of the trial. The information collected and entered in the CRD will correspond to that of the source documents.

Patients will not be identified by name on the CRD, an ID will be used coded consisting of a patient number and initials. The researcher must carry out a confidential record (patient identification list) containing information about identification of the patient included in the trial in order to keep track of the themselves if necessary.

10.3.2 Original data

The original data are those that provide evidence of the existence of the patient and they ensure the integrity of the data collected. All data on the patient's participation in the study and clinical status during the period of the study should be noted / filed in the patient's medical record. This data is defined as original data. Medical information relevant to the efficacy and safety evaluation will be transcribed to specifically designed CRDs for the study and also collected in the clinical history. During monitoring visits, consistency between stories will be checked patient clinics and CRDs, that is, verification of original data (SDV).

These, in case there is any discrepancy, must be justified.

10.4 DATA CONSERVATION AND RECORD KEEPING

All data related to the study, including the contents of the file of the study, CRDs and original data will be stored by the researcher for a period at least 15 years old. The investigator will keep a copy of each CRD and the original will be kept will send to the Promoter.

The investigator's file will contain the documents described in the ICH Directive on Good Clinical Practices.

The clinical records of the patients and other original data will be kept as much as possible period of time allowed by the hospital, institution or private practice where the performed the test. The Promoter will keep all the remaining documentation related to the trial during the period validity of the drug.

10.5 QUALITY CONTROL

During the development of the trial, monitoring visits will be carried out periodically to the centers to ensure that the protocol requirements are followed.

10.6 INSPECTIONS AND AUDITS

The Promoter, either directly or through contracted third parties, may carry out quality assurance audits at participating centers. In the event of audits, the auditor will have access to medical records, files and relevant documentation related to the clinical trial. Health Authorities may carry out inspections during the study and after its ending. In the case of audits and / or inspections, the researcher will provide all the documentation related to the study.

10.7 PRESENTATION AND PUBLICATION

All information regarding this clinical trial is considered strictly confidential and is the property of the Sponsor, who may use the Study data for scientific or commercial. Any

information related to the study will not be communicated to third parties without the prior written authorization of the Promoter.

The publication or presentation, whether complete or partial, of any part of the data or Trial results will be subject to review and written agreement with the Promoter.

11. STATISTICAL ANALYSIS

11.1 SAMPLE SIZE

As it is a phase I-II study, in which the safety of the product under study is evaluated, the sample was fixed at 12 patients per branch (24 patients in total)

11.2 STATISTICAL METHOD USED

In all descriptive analyzes, categorical variables will be summarized using frequencies and category percentages. For the distributions of continuous variables, will present the mean and its Standard Deviation, the median and the 25th and 75th percentiles of the distribution, the number of cases, minimum and maximum value.

All hypothesis tests will be two-tailed, with a significance level of 5%. The The result of a hypothesis test will comprise the 95% Confidence Interval of the variable (s) analyzed. To calculate the statistical significance of the differences between the two groups, a normality analysis of the distribution will be carried out and compare the means using the double-tailed t-test or the Wilcoxon, depending on whether the population is Gaussian or not.

11.2.1 Main objectives, main variables

- Evaluate the feasibility and safety of the use of allogeneic MSV injected into the disc space for the treatment of lumbar degenerative disc disease and pain and the disability it causes.

The variables that will be used to evaluate safety will be the AAG number related to study medication and the percentage of patients who presented a related AGS. -Evaluate the analgesic-anti-inflammatory efficacy determined by the variation of the Low back pain assessment questionnaire scores (VAS), disability (Oswestry) and health and quality of life (SF12) at 3, 6 and 12 months.

- Evaluate regenerative efficacy using quantitative MRI imaging criteria determined by the appearance of improvements in disc dehydration at 6 and 12 months.

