3.1. Main goal

□ To evaluate the viability and safety of allogeneic MSV, applied by percutaneous injection in the nucleus pulposus area for the treatment of lumbar degenerative disc disease, verifying that each of the the procedures established in the protocol and recording the possible adverse effects related to cell therapy and those that may arise for the duration of the clinical trial, whether or not related to the same.

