6.1.4 Post-treatment regime

The patient is discharged after a 2-hour observation period. Not prescribed Lumbostat corset and walking is allowed for moderate periods. Activity is suspended work for a week. Exercises to tone the muscles are prescribed para-vertebral and abdominal, which begin one month after the intervention. Medication analgesic is adapted to the needs of each patient and use should be avoided as far as possible of anti-inflammatories. Long-term follow-up will consist of clinical visits and monitoring Radiographic and MRI as specified in point 7.2 ("Schedule").

6.1.5. Possible complications derived from the proposed therapy.

The complications are the same as in the discography, and they occur very rarely. The most common complaint is exacerbation of pain for 1-2 weeks, which usually resolved by analgesia and muscle relaxants for a period short. The most serious complication is discitis, the incidence of which is less than 0.1% (Osti et al., 1990). Other complications described, although much less frequently, are transient headache, nausea, meningitis, epidural abscess, arachnoiditis, bruising intrathecal, retroperitoneal hematoma, cauda equina syndrome and acute disc herniation. Isolated cases of urticaria are not considered in this trial, as they are attributable to contrast medium. Initial fears about possible side effects of the Long-term discography regarding disc viability have not been confirmed. In a study with up to 20 years of clinical follow-up, no radiographic evidence was found of progressive disc degeneration after discography (Flanagan & Chung, 1986). The possible risk of complications derived from the use of allogeneic cells has been discussed in detail above. Suffice now to summarize that, according to the literature, the application of Allogeneic MSCs, both locally and systemically, have been shown to be safe both in the context of clinical trials and studies in animal models. Either way, will monitor skin and mucosal reactivity to watch for a possible immune reaction.

6.1.6. Methodology for obtaining bone marrow from donors.

This procedure will be applied to donors, generally included in the Eudra trial. CT2009-017405-11 (MSV_Artro) that we are carrying out or in compassionate cases authorized

by the AEMPS, and that follow the same protocol and that provide their cells left over for this test (see section 5.3).

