6.5. MANAGEMENT OF STUDY MEDICATION

The study medication, properly packaged MSV in a thermostatic container, was transported immediately after production to the application center. Has a stability longer than 12 hours at room temperature and is given as an injection in the area of the nucleus pulposus of the affected spinal segment.

7. DEVELOPMENT OF THE TEST AND ASSESSMENT OF THE RESPONSE 7.1 ASSESSMENT OF THE RESPONSE

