Interventions carried out during treatment (local injection of mepivacaine or Allogeneic MSV) derived from product infiltration are minor, and attributable to the diagnostic recording technique, namely, the risk associated with the sedation, possibility of infection or bruising, death. However, it is understood that the treatment proposed in this study does not imply risks greater than those of surgery habitual of the contemplated pathology. Rather, it involves avoiding a technique open surgical procedure and the implantation technique is the same as that used in the discography, a widely used and widely used diagnostic technique experience. Sedation and local anesthesia are assumed to maintain very high risk levels. low under conditions of good clinical practice Aside from local pain or swelling, the arm of allogeneic MSV may have theoretically immunological rejection, although, as detailed in another section, MSCs have little or no antigenic power and this type of phenomenon has not been described or in animal experiments (rabbit and pig) or in clinical trials conducted in patients with lupus erythematosus ((Sun et al., 2009; Liang et al., 2010).have obtained similar results with allogeneic mesenchymal cells derived from cord blood (Sun et al., 2010) There are also numerous treated cases of patients with breast cancer (Koc et al., 2000) graft versus host disease (Lazarus et al., 2005), and other autoimmune diseases (Bernardo et al., 2009; Bernardo et al., 2011) without that there have been, so far, adverse effects. Finally, there are 44 declared trials clinicians using allogeneic MSCs in the "clinicaltrials.gov" database for treatment of very varied pathologies, including not only graft-versus-host disease and different autoimmune diseases, but also ischemic strokes, cardiac or peripheral disorders, liver destruction, osteogenesis imperfecta or degeneration of the intervertebral disc (see

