8.4 Serious Adverse Event (AAG)

8.1.4.1 Definition

A Serious Adverse Event is any unfavorable medical event that any dosage of the product or due to specific study procedures:

□ Produces the death of the patient,

□ Threatens life,

□ Produces permanent or significant disability,

□ It gives rise to hospitalization or prolongation of it, (hospitalizations scheduled prior to patient selection or study procedures, will not be considered AAG).

□ Congenital anomalies and malignant processes.

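### Does the plan have to define which serious adverse events count as related before its main safety counts can be relied on?

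*Combined protocol and SAP*

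**What the plan says.** Section 11.2.1 says that safety will be evaluated by "the AAG number related to study medication and the percentage of patients who presented a related AGS". AAG is the document's abbreviation for a serious adverse event; AGS appears nowhere else in this sense and is evidently a slip for it.

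The main goal in section 3.1 is wider. Adverse effects are to be recorded throughout the trial, "whether or not related to the same". The definition of a serious event in section 8.1.4.1 covers events with "any dosage of the product or due to specific study procedures".

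Section 8.2 asks the responsible researcher to grade the causal relationship in five steps: not related, unlikely, possible, probable, true. No section converts that scale into a yes or no for the analysis.

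**The concern.** Both named variables depend on the word related, and it seems to be left open in two ways.

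- **Cut-off.** A serious event graded possible could be counted or left out, and the choice could be made after the data are seen.
- **Scope.** Section 6.5 uses the term for the cells alone: "The study medication, properly packaged MSV in a thermostatic container". Section 8.2 says that risks "derived from product infiltration are minor, and attributable to the diagnostic recording technique". On that reading, a serious event caused by the needle rather than the cells would fall outside the count. The arms differ in this respect: sections 4.2 and 6.1 give the experimental arm a disc puncture and the control arm a paravertebral injection, so assigning events to technique could remove them unevenly.

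The headline safety result of a safety trial would then rest on a judgement that the plan does not fix in advance. The documents do not say that the person making the judgement is masked.

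**Working it through.** The plan gives no figure to reproduce: section 11.1 fixes 12 patients per arm without a calculation, and no serious event rate is stated. The check is therefore a reading of the text, with arithmetic for scale.

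**1. Scope, passages side by side.**

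- Narrow reading: section 6.5, which is a transport and handling paragraph and not a definition, and the sentence in section 8.2 about technique, whose translation is hard to follow.
- Wide reading: section 8.2 says that what is graded is causality between the treatment and the event, and it speaks of "Interventions carried out during treatment (local injection of mepivacaine or Allogeneic MSV" in each arm. Section 6.1.5 describes the puncture complications under the title "Possible complications derived from the proposed therapy". The objective printed directly above the safety variables in section 11.2.1 refers to cells injected into the disc space. The Annex IV instructions count both product and control as investigational medicine, although they do not mention the puncture.

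The wide reading is better supported, though it is not stated outright.

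**2. Cut-off.** Nothing in the documents settles it. The phrase in section 8.1.4.2 about reactions that may be related to the drug governs reporting to the authorities, not this analysis.

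**3. What one reclassified event does.** Exact (Clopper-Pearson) 95% limits with n = 12:

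- 0/12: upper limit = 1 − 0.025^(1/12) = 26.5%.
- 1/12 = 8.3%: lower limit = 1 − 0.975^(1/12) = 0.2%; upper limit = 97.5% quantile of Beta(2, 11) = 38.5%.

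The 26.5% limit comes from the sample size and holds under any definition of related.

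**4. How likely a serious puncture event is.** Section 6.1.5 states: "The most serious complication is discitis, the incidence of which is less than 0.1" per cent. At that ceiling:

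- 12 punctures: 1 − 0.999^12 = 1.2%.
- 24 punctures (two discs in every patient, assuming the rate is per disc): 1 − 0.999^24 = 2.4%.

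**5. How likely a serious event of any cause is.** The documents give no rate. At assumed rates of 2%, 5% and 10% per patient over 12 months, the chance of at least one in 12 patients is:

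- 1 − 0.98^12 = 21.5%
- 1 − 0.95^12 = 46.0%
- 1 − 0.90^12 = 71.8%

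These are upper bounds on the chance of a disputed event, because events graded not related or true fall on the same side of any reasonable cut-off. Only the grades between them can move.

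**6. What is reported whatever the definition.**

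- Section 8.3 logs every event from consent, regardless of attributed cause.
- Section 8.1.4.2 sends every serious event to the CRO regardless of cause, with a causality statement.
- Section 11.3.6 lists all adverse and serious adverse events with relationship and severity, and gives the frequency and percentage of each without a causality filter.

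**The case for a change.** The strongest case for a change is that safety is the main objective, the named variables are the related counts, and a rule fixed in advance is better than one chosen later by a rater who may know the allocation. The unfiltered tables in section 11.3.6 do not define related and are not stated to be by arm. Defining the term would take a few lines and no new data. One could go further and make serious events of any cause the main count.

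It stands that the cut-off is missing and that the scope is implied rather than written. It does not follow that the safety conclusion is at risk. The listings carry each event's causality grade, so with 24 patients a reader can recount under any cut-off, and an analyst of a two-arm trial would tabulate by arm without being told. Promoting the all-cause count would only re-rank a figure that section 11.3.6 already produces. It would also make the headline less specific to the product, so leading with related events and printing the unfiltered tables beside them is a fair choice.

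Masking is a separate matter. The Summary masks the patient and those analysing the results but leaves the applying doctor open, while section 11.5 leaves researcher blinding for the future. That tension is not a defect of the safety variable.

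**Conclusion.** No change follows. The plan leaves a definitional detail unstated, but everything needed to fill it is collected and reported. One disputed patient would move the related percentage by 8.3 points, and the exact intervals for 0/12 and 1/12 overlap almost entirely. At the protocol's own discitis ceiling, the chance of a puncture case that turns on scope is about 1.2% to 2.4%. How often the cut-off would matter cannot be estimated from the documents, because they give no serious event rate and no distribution of causality grades.

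This conclusion assumes that sections 8.3 and 11.3.6 are followed as written, that the analysts state the cut-off they use, and that the tables are split by arm, as is usual in a two-arm trial.
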